### 6.2.2 Sample

In Florida, only 4.3 percent of children ages 11 to 17 are current cigarette smokers. However, e-cigarette use is increasing from 5 percent of Florida high school students in 2013 to 11 percent in 2014. While the percentage of adolescents at risk to begin smoking is not known, studies have identified maternal smoking, trying tobacco, alcohol or marijuana by 8th grade, and endorsement of sensation seeking behavior as risk factors for tobacco and related product use. Children should be screened for these risks.

We will screen all youth, ages 11 through 17 years, in the practice for current tobacco use and risk behaviors associated with cigarette and nicotine product use with the goal of reaching 20 children per practice who are current tobacco users who could receive at least one or more of Steps 3 through 6 (advise, assess, assist, arrange). To achieve 20 patients per practice who reach the “advise” and “assess” stages, if the practice had the average percentage of children using e-cigarettes, approximately 218 patients would need to be screened. The number screened to reach the “advise” and “assess” stages is based on the e-cigarette use and not the traditional cigarette use.

Intervention practices will be asked to screen patients for tobacco and nicotine product use (using the anticipate and ask components of the 6As) by having youth complete a tobacco and nicotine use screening tool until the practice has identified and completed at least the “advise” and “assess” intervention on 20 tobacco/nicotine users. Parental consent and adolescent assent will be electronically obtained using ResearchActs software. In addition, practices will be asked to implement a short parental screening tool for tobacco use. The parent and child will respond to the surveys separately. After the child completes the survey s/he will be offered a \$5 electronic Amazon gift card.

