Practices will be asked to identify a location in the waiting room or an exam room where the screening tool can be completed without the parent present. Completing the tool is expected to take 10 minutes of the youth's time and 10 minutes of the parent's time, inclusive of the time to complete the informed consent. We estimate practices will need to participate in the project for approximately 6 months. This time period includes baseline and follow-up data collection, study implementation, and participant accrual. The 6-month time period is also necessary for those practices who wish to use the project for participation in their Maintenance of Certification (MOC) requirements.

The total duration of study participation for the practices is estimated to be 10 months. This includes a 3-month start up period, a 6-month intervention (or control) time period and a 1-month follow-up. The 6-month intervention period is necessary for those practices who want to use the study participation to assist them in meeting their MOC requirements. For practices not participating in the MOC Program, the intervention period is finished when 20 patients complete at least the “advise” and “assess” components.

Practices can make some modifications to the intervention to fit with their workflow. For example, some practices have nursing staff screen for tobacco/nicotine use and make recommendations about cessation strategies. Other practices have physicians provide the screening and counseling. Practices can make adaptations regarding who administers the 6As but they must follow the 6A intervention. Any type of primary care visit can be used to conduct the 6As.

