The duration of the study participation for patients is variable. For those who do not smoke/use nicotine products or who smoke/use nicotine products but do not want to quit, the duration of the study is the baseline data collection (5 to 10 minutes for the youth and 5 to 10 minutes for the parent, inclusive of the informed consent), clinician screening and advising (2 to 5 minutes for the child and 2 to 5 minutes for the parent), and the follow-up telephone survey administered through the UF Survey Research Center (10 minutes) for a total estimated participation time of approximately 25 to 30 minutes. Adolescent participants will be offered another \$5 electronic Amazon gift card after completion of the follow-up telephone survey. For patients who smoke/use nicotine products and want to quit, their participation is an estimated 35 minutes for baseline and follow-up telephone survey data collection and provider discussion during the primary care visit. Practices can customize who conducts the screening and advising. For example, some practices assign that role to the nursing staff. In other practices, the clinician seeing the patient for the visit provides this screening and counseling himself or herself.

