D. Parent Brief Questionnaire (PBQ – Appendix D): The PBQ was developed using questions recommended by the American Academy of Pediatrics. Parents are one of the most important sources of a child's tobacco smoke exposure. Therefore screening parents is a recommended best practice. The PBQ will also be administered using ResearchACTS.

E. 6As and Best Practices Medical Record Review Form (6As MRR - Appendix E): At baseline, we will request the (Medical Record Number) MRN from the Integrated Data Repository (IDR) for 75 randomly selected patients from both control and intervention practices in Gainesville and Jacksonville, which will be reviewed for 1) adherence to the 6As (through whichever number of steps are applicable for that patient) inclusive of tobacco and nicotine product use and 2) parental screening for tobacco use. Specifically, the IDR will be asked to select MRNs from 75 records consecutively from well care visits from participating providers for patients 11 through 17 years of age from the 6 months prior to the start of the study until they reach 75 records. OneFlorida has a medical record review team with certified medical record coders. The medical record review team will measure compliance with the 6As and parental screening using the review tool. At the end of the intervention period, we will request the medical records for those patients participating in the intervention. We will request MRNs from the IDR for control group practices and review 75 consecutive medical records for patients ages 11 through 17 years seen during the 6 month study period.

[name] will train the medical record reviewers for the Gainesville and Jacksonville sites. Interrater reliability will be established and training will continue until there is 98% agreement between reviewers. During the record review process, [name] will be available to the reviewers to respond to questions. If there is not 98% agreement among the medical record reviewer findings, the medical record reviewers will undergo additional training from [name]..

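### Follow-up charts for the primary outcome are drawn by different rules in the two arms, so the contrast estimates practice-level adherence only if nearly all eligible youth participate and visit mix matches

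*Combined protocol and SAP*

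**What the plan says.** Item E of section 6.2.3 contains three chart rules.

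- **Baseline, both arms.** The data repository supplies "75 records consecutively from well care visits from participating providers for patients 11 through 17 years of age", from the six months before the study. The item also calls these records randomly selected, but it does so for both arms alike.
- **Follow-up, intervention practices.** "At the end of the intervention period, we will request the medical records for those patients participating in the intervention". No number, ordering, visit type or provider limit is given, and participation is not defined for this purpose.
- **Follow-up, control practices.** The team will "review 75 consecutive medical records for patients ages 11 through 17 years seen during the 6 month study period". No participation filter applies, and the baseline limits to well-care visits and participating providers are not repeated.

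Section 6.2.2 describes entry in the intervention practices. The aim is broad: "We will screen all youth, ages 11 through 17 years, in the practice for current tobacco use". Entry nevertheless passes through consent: "Parental consent and adolescent assent will be electronically obtained using ResearchActs software". Visit type is open: "Any type of primary care visit can be used to conduct the 6As".

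Section 6.2.5 takes the primary outcome, clinician adherence to the 6As, from these charts. It names three measures: discussion of the patient's tobacco use, advice to quit, and discussion of the parent's tobacco use. The models adjust for age, gender, race and clinic. Section 6.2.4 makes the practice the target of the intervention, and Figure 2 lists practice compliance among the outcomes.

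**The concern.** A practice-level question needs a sample of the practice's eligible visits in both arms. Here the intervention arm contributes only youth who were reached and agreed, while the control arm contributes whoever was seen. Any gap in documented adherence between participants and non-participants enters the group contrast as if it were an effect of the intervention.

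The planned model cannot remove it. It has no term for participation, visit type or provider, and charts of non-participants in intervention practices are never requested, so the practice-wide rate cannot be rebuilt afterwards.

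Other differences may come with it. Participants can come from any type of visit. The calendar window may also differ: the control rule refers to the six-month study period, but "For practices not participating in the MOC Program, the intervention period is finished when 20 patients complete at least the" *advise* and *assess* steps.

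Aim 2 is to gather pilot data on effectiveness. A contrast with a bias of unknown sign and size is a poor guide to a later trial.

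**Working it through.** **Who counts as participating.** The wider reading is all enrolled youth. Section 6.2.2 sets out study participation for non-users too: "For those who do not smoke/use nicotine products or who smoke/use nicotine products but do not want to quit, the duration of the study" is followed by their time commitment. Item E of section 6.2.3 scores adherence through the steps that apply to each patient, which presupposes patients at different steps. The narrower reading is the 20 users per practice who completed *advise* and *assess*; section 6.2.2 uses that count as an accrual goal and stopping point. The text favours the wider reading, which is used below.

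**Participation error.** The plan gives no figure to reproduce here: the 75 has no derivation and reach is not stated. Let r be the share of eligible youth who participate, and p1 and p0 documented adherence in participants and non-participants of the intervention practices.

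- Practice-wide rate: r·p1 + (1 − r)·p0
- Rate in the planned charts: p1
- Error: p1 − [r·p1 + (1 − r)·p0] = (1 − r)(p1 − p0)

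All values of r, p1 and p0 here are assumed:

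| r | p1 | p0 | Error, points |
|---|---|---|---|
| 50% | 80% | 50% | 0.50 × 30 = +15 |
| 50% | 80% | 65% | 0.50 × 15 = +7.5 |
| 75% | 80% | 70% | 0.25 × 10 = +2.5 |
| 100% | any | any | 0 |
| 75% | 60% | 70% | 0.25 × (−10) = −2.5 |
| 50% | 60% | 70% | 0.50 × (−10) = −5 |

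Positive values are plausible because participants have just completed the tobacco questionnaire and their answers drive the prompts. The second row shows the error shrinking if training also improves care of non-participants. Negative values are possible because the prompts sit in ResearchACTS, while reviewers read Epic or PDF records. Clinicians who rely on the former may write less in the latter. These values illustrate and do not bound the error: lower reach or a wider gap would enlarge it.

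**Visit mix.** Assume no true effect, with adherence of 60% at well visits and 20% at others. The spurious difference is 40 points times the difference between arms in the share of well visits. If intervention charts are all well visits and control charts are 80%, 50% or 30% well visits, it is 40 × 0.20 = 8, 40 × 0.50 = 20 or 40 × 0.70 = 28 points. The sign reverses if the intervention charts hold fewer well visits.

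**Scale.** Take items scored on every chart, rates near 50%, 2 × 190 = 380 intervention charts (190 per practice is the number section 6.2.3, item C, expects to ask, not the number enrolled) and 2 × 75 = 150 control charts.

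- Under the plan's independence assumption: SE = √(0.25/380 + 0.25/150) = 4.8 points, so +15 is 3.1 SEs, +2.5 is 0.5 and −5 is −1.0.
- With an assumed intraclass correlation of 0.01, the design effects are 1 + 189 × 0.01 = 2.89 and 1 + 74 × 0.01 = 1.74. SE = √(0.25 × 2.89/380 + 0.25 × 1.74/150) = 6.9 points, so +15 is 2.2 SEs.
- With 0.05, the design effects are 10.45 and 4.70, the SE is 12.1 points, and +15 is 1.2 SEs.

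**Denominator for advice to quit.** Section 6.2.5 names advice to quit, but Appendix E item 5 asks whether the youth was advised not to use products and carries no user condition, unlike items 2, 3, 6 and 7. If the measure is limited to users, 75 charts hold about 75 × 0.043 = 3.2 to 75 × 0.11 = 8.3 of them, at the cigarette and e-cigarette prevalences in section 6.2.2. If item 5 supplies it, all charts count.

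**The case against.** The best defence is the stated aim of screening every youth aged 11 to 17. If that were met, r would be close to 1 and the participation error close to zero. That stands as a condition, but not as an assurance: consent and assent are required, section 7 makes taking part voluntary, and no section plans to measure reach. Full reach would also leave any difference in visit type, provider or window.

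Second, this is a pilot in four convenience-sampled practices with no power claim, and participants' charts are needed for Aim 3 in any case. Both points are fair. They argue for keeping those charts, not for using them as the intervention side of the primary comparison when section 6.2.5 plans a formal between-group model.

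Three stronger readings are tempting, and the documents do not support them.

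- *The effect will be inflated, or the contrast cannot estimate practice-level adherence.* No document gives reach or adherence by participation, and the sign could be negative.
- *The advice measure is selected on itself.* This would follow if only users who completed *advise* and *assess* counted. With full documentation and no true effect, the difference would be 100 − 81 = 19 points if the clinician-level 81% in section 4 were the usual rate. The text favours the wider reading, 81% is not a chart rate, and full documentation is itself doubtful.
- *Advice to quit rests on a handful of users and should be demoted.* Appendix E item 5 leaves the denominator open, so this is not established.

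**Conclusion.** The defect holds: the two arms have different follow-up chart rules for the primary outcome, after a common rule at baseline, and neither the covariates nor any other section repairs this. The contrast estimates practice-level adherence only under near-complete participation and matching visit mix, and the plan checks neither.

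The size is conditional. On assumed inputs the participation error lies between about −5 and +15 points, and visit mix could add a difference in either direction. The top of that range is large against a 4.8-point standard error, but that figure treats charts within four practices as independent. With modest clustering the same error is about 1.2 to 2.2 standard errors.

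Confidence is high that the rules differ and low about the direction and amount of bias. The sampling rule should be corrected before the follow-up charts are requested.

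**What to change.** For the primary comparison, draw follow-up charts in all four practices by the baseline rule regardless of enrolment: consecutive well-care visits with participating providers, ages 11 to 17, the same number per practice and the same calendar window. Say that other visit types fall outside this set. Use it for all three primary measures.

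In addition:

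- Define participation in item E of section 6.2.3; one line settles which reading applies.
- Report reach: participants divided by eligible youth seen.
- State the denominator for advice to quit and reconcile section 6.2.5 with Appendix E item 5. If it is limited to users, report the item with its imprecision.
- Report participants' charts separately, for fidelity and Aim 3.
- State whether 75 is per practice, per arm or in total, and whether baseline selection is random or consecutive.

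The cost is protocol wording plus extra reviews in the two intervention practices by the existing team, repeating the baseline repository request: 2 × 75 = 150 if 75 is per practice, 75 if per arm, about 38 if in total. The sponsor must also confirm that the record-review permission used for baseline and control charts covers non-enrolled youth in intervention practices, including those who declined; the documents reviewed here do not settle this. The observed effect will probably be smaller.

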#### **6.2.4 Intervention**

Figure 2 shows a summary of the overall study and intervention. The following steps will be used to implement the intervention:

1. **Baseline Data:** Intervention and control practices will complete the Clinician and Practice Surveys and participate in the medical record review. They also will be asked to provide copies of any youth and parent health risk assessment or screening tools used in their practices related to tobacco and nicotine products.

2. Tobacco and Nicotine Product Screening: The intervention practices will receive the implementation supports listed in Figure 2. Intervention practices can make modifications to the study protocol to fit with their workflow, while maintaining the scientific integrity of the study. The steps for administering the TPNQ and Parent Brief Questionnaire (PBQ) using the ResearchACTS software at the point of care was described in the preceding *Data Collection* Section. As previously noted, the intervention is focused on the practice and not on the youth or the parents per se. Future studies will explore options related to implementing interventions and supports for youth related to tobacco and nicotine product cessation.
3. The control sites will deliver their usual care.
4. Upon study completion, implementation and control sites will complete the Clinician and Practice Surveys, participate in the medical record review, and have child reported outcomes results.

**Figure 2. Study Overview and Intervention**

Intervention Practices N=2	Control Practices N=2
Baseline	Baseline

 
• Complete Clinician and Practice Surveys
 
• Usual Care Documentation
 
• Medical Record Reviews
 
	
 
• Complete clinician and Practice Surveys
 
• Usual Care Documentation
 
• Medical Record Reviews
 

The Intervention	Usual Care

 
• Protocol Adaptation
 
• ResearchACTS –TPNQ,6As Prompts, Parent Screening & Registry
 
• Practice Facilitators
 
• MOC support
 
	
 
• Tobacco and Nicotine Screening & Counseling
 

Outcomes	Outcomes

 
• Practice Compliance
 
• Child Reported Visit Outcomes
 
• Clinician and Practice Changes
 
	
 
• Practice Compliance
 
• Child Reported Visit Outcomes
 
• Clinicians and Practice Changes
 

	Post Study
	
 
• Support for MOC
 

### 6.2.5 Analysis Plan

Intervention effect on clinician adherence to the 6As: The primary outcome is clinician adherence to the 6As inclusive of tobacco and nicotine product use as collected in the medical records. During both the baseline and follow-up periods, we will request and review medical records to identify the following primary outcome measures: discussion of patient’s tobacco use, advice to quit, and discussion of parent’s tobacco use. Since this is a pre-post design with one intervention group and one control group, we will perform ANCOVA-type analyses assuming that the patients and providers are independent of each other. For each outcome, we will fit a logistic regression model in which the dependent variable is the post-intervention measure of the outcome. The main independent variables will be the pre-intervention measure of the outcome, group (binary: intervention vs. control), and pre-intervention measure by group interaction. In all models, we will also control for age, gender, and race, and clinic (multi-nominal: clinics 1-4). The model building process will follow guidelines provided by Hosmer and Lemeshow.

Intervention effect on practice characteristics: Practice characteristic data will be measured from the Change Process Capability Questionnaire and the Adaptive Reserve Questionnaire (Appendix B). We will collect the practice characteristic data twice, once at baseline and once at 9 months. Therefore, we will fit ANCOVA models for data analysis, assuming the practices are independent of each other. The characteristics include meeting frequency, clinician/staff performance evaluation, and planned communication. The primary predictor of interest is group (intervention vs. control). The model building process will follow guidelines provide by Muller and Fetterman. We will perform residual analysis to check the normality assumption of the models. We will perform box-cox transformation if there is a violation of the normality assumption.

Congruence between documentation of the intervention in the EHR and adolescent report of the intervention: Within 30 days post primary care visit, patients will be contacted via telephone to complete the Tobacco and Nicotine Product Primary Care Questionnaire (TNP-PCQ) (Appendix E), which asks about their recollection of the tobacco and nicotine product discussions with their providers during the primary care visit. For each outcome in the TNP-PCQ survey, we will perform a concordance analysis to evaluate the agreement between the medical record review data and patient-reported data. Concordance will be evaluated using the following statistics: sensitivity, specificity, positive predictive value (PPV), negative predictive value (NPV) and the Kappa statistic. Differences in concordance will be tested with the Pearson chi-square test.

**7. Possible Discomforts and Risks.** There are no known risks associated with this study. The only discomfort that the patient may experience may be associated with discussing something that is personal. Patients will be reminded that they can skip any question on the survey questionnaire that they wish. Patients will be informed that they can choose not to participate in in any portion of the discussion and that answering questions is completely voluntary. There is minimal risk in working with personal health information. However, all data will be in a secure database with access limited to a programmer and the study members conducting data analysis. The medical records will be reviewed onsite and will not leave the practice setting or will be reviewed through a secure computer access if permission is granted for UF Health sites.

**8. Possible Benefits.** There are no potential benefits to patient participation.

**9. Conflict of Interest.** None.

**10. Data Plan.** Precautions will be made to protect participant privacy in the clinic and in the data storage. In the clinic, participants will complete the survey on iPads. The iPad are used to assess the survey website that is stored on a secure server and maintained by UF. No data is stored on the iPads. Identifiable data collected will only be used during the retrospective record review portion of the study. This data will be stored on secure UF servers only accessible to the minimal necessary study staff. Individually identifiable information will not be released to anyone outside the project. After the record review portion of the study is complete any and all identifiable data will be removed from ResearchACTS. Upon closure of the study, data will be de-identified and any study information will be encrypted and labeled with a date for destruction 6 years after the IRB approval date of the study closure.

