## 6.2 Methods

### 6.2.1 Study Design

This study will be implemented with a convenience sample of 4 pediatric primary care practices. Two will be randomly assigned to receive the intervention and two will serve as the comparison groups. Two of the practices will be located at UF Health in Gainesville and two will be located at UF Health in Jacksonville. The control group will provide their usual care related to tobacco and nicotine product use screening and cessation recommendations. The control group will be given the opportunity to participate in the intervention following study completion.

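### The primary analysis assumes independent patients and providers although four whole practices are randomised, so its standard errors are too small by an amount that depends on the ICC and charts per practice

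*Combined protocol and SAP*

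**What the plan says.** Section 6.2.1 of the combined protocol and SAP describes the design: "This study will be implemented with a convenience sample of 4 pediatric primary care practices", and "Two will be randomly assigned to receive the intervention and two will serve as the comparison groups". Section 6.2.4 places the intervention at the same level: "the intervention is focused on the practice and not on the youth or the parents per se".

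Section 6.2.5 makes clinician adherence to the 6As, taken from medical records, the primary outcome. It has three measures: discussion of the patient's tobacco use, advice to quit, and discussion of the parent's tobacco use. The analysis is stated as follows: "we will perform ANCOVA-type analyses assuming that the patients and providers are independent of each other". The model is then given: "For each outcome, we will fit a logistic regression model in which the dependent variable is the post-intervention measure of the outcome". Its terms are the pre-intervention measure, group, their interaction, age, gender, race and a four-level clinic variable.

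For this outcome the documents contain no random effect, GEE, cluster-robust variance, design effect, ICC or practice-level test. They state no alpha and no power.

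**The concern.** Charts from one practice share clinicians, workflow and documentation habits, and Section 6.2.2 lets each practice decide who delivers the 6As. Outcomes within a practice are therefore likely to be correlated. The design has only four independent units, whereas the stated analysis counts each chart as one.

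The stake is that a chance difference between two pairs of practices is reported as an intervention effect, with an interval that is too narrow. Aim 2 seeks pilot data on effectiveness, so these estimates are likely to inform a larger study. An assumption that fixes the correlation at zero would carry over with them.

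**Working it through.** **Inputs.**
- Four practices, two per arm (6.2.1).
- Control follow-up charts: 75 (6.2.3 E), taken as per practice. The baseline wording in the same item can also be read as 75 over all practices, 75/4 ≈ 19 each. I use 19 in both arms as a low-end case.
- Intervention follow-up charts: those of all participating patients (6.2.3 E), about 190 per practice (6.2.3 C) or 218 (6.2.2).
- Users only, for advice to quit: 20 per intervention practice (6.2.2). For control practices I assume 75 × 0.11 ≈ 8, using the 11% e-cigarette figure in 6.2.2.
- Assumptions not in the documents: ICC 0.01 to 0.05; two-sided alpha 0.05; clinic left out so that group can be estimated.

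**Plan's own figure.** There is none for this comparison. The 218 is a recruitment target, and it does not follow from the stated inputs: 20/0.11 = 182. It equals 182 × 1.2, but no such allowance is stated. That is a separate matter; 218 serves here only as a possible cluster size.

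**Step 1, design effect.** DE = 1 + (m − 1) × ICC. For m = 75: 1 + 74 × 0.01 = 1.74, and 1 + 74 × 0.05 = 4.70.

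**Step 2, ratio of true to naive SE.** R = √[(DE_C/m_C + DE_I/m_I) / (1/m_C + 1/m_I)]. Example, 75 v 190 at ICC 0.01: DE is 1.74 and 2.89, so R = √[(0.0232 + 0.0152)/(0.0133 + 0.0053)] = 1.44.

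**Step 3, actual type I error** = 2 × [1 − Φ(1.96/R)].

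| Charts per practice, control / intervention | R, ICC 0.01 | Type I | R, ICC 0.05 | Type I |
|---|---|---|---|---|
| 75 / 75 | 1.32 | 13.7% | 2.17 | 36.6% |
| 75 / 190 | 1.44 | 17.3% | 2.52 | 43.6% |
| 75 / 218 | 1.45 | 17.7% | 2.56 | 44.3% |
| 19 / 19 | 1.09 | 7.1% | 1.38 | 15.5% |
| 8 / 20 (users only) | 1.05 | 6.2% | 1.23 | 11.2% |

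Beta-binomial simulations of an unadjusted patient-level test, at base rates from 0.3 to 0.6, agree. At ICC 0.01 and 0.05 they give 13% to 15% and 37% to 38% for 75 / 75, and 17% to 18% and 44% to 45% for 75 / 190. A t-test on practice rates (2 df) stays at about 5% to 6%.

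**Step 4, the model with clinic.** Intercept, group and three clinic dummies make 5 columns of rank 4, so group is fully determined by clinic. If software drops one clinic dummy, the group coefficient compares one intervention practice with one control practice. Simulated type I error is then about the same: 17% and 45% for 75 / 190.

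**Step 5, the baseline measure.** Baseline charts come from the 6 months before the study, and nothing pairs them with follow-up charts. The baseline can therefore enter only as a practice-level value. Intercept, group, baseline and interaction are 4 parameters for 4 practices, leaving 0 practice-level degrees of freedom.

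**Step 6, what 2 v 2 can support.** The critical t on 2 df is 4.30 instead of 1.96. There are C(4,2) = 6 allocations, so the smallest two-sided exact randomisation p is 2/6 = 0.33 (2/4 = 0.50 if randomised within city).

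**Step 7, interval for the between-arm difference in change.** Take p = 0.6, ICC 0.02, and 75 baseline and 75 follow-up charts per practice; p(1 − p) = 0.24.
- Naive: 1.96 × √(2 × 0.24/75) = 1.96 × 0.080 = ±16 points.
- Practice effects fully stable over time: 4.30 × √(2 × 0.24 × 0.98/75) = 4.30 × 0.079 = ±34 points.
- Practice effects independent between periods: 4.30 × √(2 × 0.24 × 2.48/75) = 4.30 × 0.126 = ±54 points.

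**The case against.** The plan states its assumption openly, calls the study a pilot, and sets no significance level. It includes clinic in the model, and baseline and patient covariates might lower the residual correlation. The calculations above are for an unadjusted comparison, not the full planned model. No re-analysis makes two practices per arm informative.

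Much of this stands, and it limits the point. A reader might infer that the standard errors are far too small for every primary measure. The documents do not support that: they give no ICC, the 75 charts can be read two ways, and for advice to quit among users the inflation is modest. A reader might also infer that Appendix E rules out any clinician-level analysis because it prints no clinician field. It prints no age, gender, race or clinic field either, although the model uses all four, so the printed list is not the whole dataset. Records are selected "consecutively from well care visits from participating providers for patients 11 through 17 years of age", so the provider is known at selection. Nor do the documents make an ICC an objective.

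The clinic term is no defence. Kept in full, it removes the arm comparison; partly dropped, it leaves between-practice variation out of the standard error. In either case correlation within clinician is ignored. The pilot label does not help either, since Section 6.2.5 still models an intervention effect for each measure.

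**Conclusion.** The independence assumption contradicts the design and should not stay. The direction is certain for any positive within-practice correlation. The size is conditional on the assumed ICC of 0.01 to 0.05, a two-sided 5% test, and clinic being left out. Type I error then runs from slightly above nominal (about 6% to 11% for users only; 7% to 16% at about 19 charts per practice) to several times nominal (about 14% to 38% at 75 per practice; 17% to 44% at 190 v 75). With the clinic term as written, the question of size does not arise, because no arm-level effect can be estimated. With two practices per arm, a significant patient-level result would rest on the independence assumption and not on the randomisation.

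**What to change.** In Section 6.2.5, delete the independence assumption and do not enter clinic as a fixed effect alongside group. For each primary measure, report each practice's baseline and follow-up rates with their denominators. Give the between-arm difference in practice-level change with a t interval on 2 df. Label it as pilot estimation and make no significance claim.

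Record a clinician code when charts are abstracted, because the Data Plan removes identifiers after the record review. Report ICCs descriptively, noting that with four practices they will be imprecise.

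The cost is SAP wording, one extra code per chart, and wider intervals of the order shown in Step 7. That width reflects what four practices can show; the design itself need not change.
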